Official Title: A Phase 3, Randomized, Double-blind, Multicenter, Placebo-controlled, Parallel-group Trial Evaluating the Efficacy, Safety, and Tolerability of Centanafadine Sustained-release Tablets in Adults With Attention-deficit/Hyperactivity Disorder

NCT Number: NCT03605836

Document Date: Protocol Version 4.0: 15 January 2020

Otsuka Pharmaceutical Development & Commercialization, Inc

Investigational Medicinal Product

Centanafadine (EB-1020)

REVISED CLINICAL PROTOCOL

A Phase 3, Randomized, Double-blind, Multicenter, Placebo-controlled, Parallel-group Trial Evaluating the Efficacy, Safety, and Tolerability of Centanafadine Sustained-release Tablets in Adults with Attention-deficit/Hyperactivity Disorder (Trial 405-201-00014)

Protocol No. 405-201-00014

IND No. 119361

CONFIDENTIAL – PROPRIETARY INFORMATION

Clinical Development Phase:	3
Sponsor:	Otsuka Pharmaceutical Development & Commercialization, Inc. [name]
Immediately Reportable Event	Syneos Health Research Pharmacovigilance & Drug Safety Fax: [REDACTED] E-mail: [REDACTED]
Issue Date:	8 Mar 2018
Date of Amendment 1	18 May 2018
Date of Administrative Change 1	30 Aug 2018
Date of Amendment 2	15 Jan 2020
Version No.:	4.0

Protocol 405-201-00014

Protocol Synopsis

Name of Sponsor: Otsuka Pharmaceutical Development & Commercialization, Inc. Name of Investigational Medicinal Product: Centanafadine (EB-1020)		Protocol No.: 405-201-00014 IND No.: 119361
Protocol Title:	A Phase 3, Randomized, Double-blind, Multicenter, Placebo-controlled, Parallel-group Trial Evaluating the Efficacy, Safety, and Tolerability of Centanafadine Sustained-release Tablets in Adults with Attention-deficit/Hyperactivity Disorder (Trial 405-201-00014)	
Clinical Phase/Trial Type:	3	
Treatment Indication:	Adult Attention-deficit/Hyperactivity Disorder (ADHD)	
Objective(s):	
Primary: To confirm the efficacy of centanafadine sustained-release (SR) tablets administered twice-daily (BID; 200 mg or 400 mg total daily doses [TDDs]) compared to placebo in the treatment of adults with ADHD
 
Secondary: To confirm the safety and tolerability of centanafadine SR tablets administered BID (200 mg or 400 mg TDDs) compared to placebo in the treatment of adults with ADHD
	
Trial Design:	
This trial is a phase 3, randomized, double-blind, multicenter, placebo-controlled, parallel-group trial to confirm the efficacy, safety, and tolerability of centanafadine SR (200 mg TDD or 400 mg TDD) compared to placebo for the treatment of adults with ADHD.
 
The trial will have 4 periods: (1) screening and washout; (2) 1-week single-blind placebo run-in; (3) 6-week double-blind treatment; and (4) 7-day follow-up period (follow-up telephone calls at 1, 3, and 5 days after the last dose of investigational medicinal product (IMP), and in-clinic visits 2 and 7 days after the last dose of IMP) for subjects who complete the trial, and decide to enroll in Trial 405-201-00015. For subjects who terminate early, decide to not enroll in Trial 405-201-00015, or who are not eligible to enroll in Trial 405-201-00015, they will be required to participate in the 7-day follow-up period as well as participate in an additional follow-up telephone call 10 days after the last dose of IMP. Subjects randomized to receive a TDD of 200 mg centanafadine SR will start at their target dose at the start of the double-blind treatment period.
	

Protocol 405-201-00014

	
Subjects randomized to receive 400 mg TDD centanafadine SR will start the double-blind treatment period at the TDD of 200 mg centanafadine SR for 7 days, before they are escalated to their target TDD of 400 mg for a total of approximately 42 days of treatment. Subjects will be required to visit the site up to 12 times over the trial.
 
Subjects who complete both the 6-week double-blind treatment period and the 7-day follow up (follow-up telephone calls at 1, 3, and 5 days after the last dose of IMP, and in-clinic visits 2 and 7 days after the last dose of IMP), and refrain from using prohibited medications after the IMP is stopped may be eligible to enroll into Trial 405-201-00015, which is a 12-month, observational, open-label trial to evaluate the long term safety and tolerability of subjects with ADHD who previously participated in Trials 405-201-00013 or 405-201-00014. Subjects who terminate early, decide to not enroll in Trial 405-201-00015, or who are not eligible to enroll in Trial 405-201-00015, will be required to participate in the 7-day follow-up period as well as participate in an additional follow-up telephone call 10 days after the last dose of IMP. For subjects who early terminate or decline participation in the open-label trial, they will be instructed to refrain from utilizing prohibited concomitant medications (Section 4.1), including ADHD treatments, until after the follow-up telephone call 10 days after the last dose of IMP.

Subject Population:	
A total of up to 1150 male and female subjects with current diagnosis ADHD and between the ages of 18 and 55 years, inclusive, are planned to be screened in order to randomize approximately 450 subjects to yield 292+ completers.
 
Subjects must meet the Diagnostic and Statistical Manual of Mental Disorders Fifth Edition (DSM-5) criteria for ADHD (including predominantly inattentive presentation, hyperactive presentation, or combined presentation) as confirmed by the Adult ADHD Clinical Diagnostic Scale (ACDS) Version 1.2. To confirm that ADHD is the primary diagnosis, the Mini International Neuropsychiatric Interview (MINI) will be used to identify and exclude other psychiatric conditions which would preclude enrollment.

Protocol 405-201-00014

	
Subjects who were not receiving any pharmacological treatment for ADHD must have an Adult ADHD Investigator Symptom Rating Scale (AISRS) score of ≥ 28 at screening and baseline. Subjects who were receiving pharmacological treatment for ADHD at screening must have a minimum AISRS score of ≥ 22 at screening, and a score of ≥ 28 at baseline.
 
All subjects must be willing to discontinue all prohibited psychotropic medications (Section 4) starting from the time of signing the informed consent through the 7-day follow-up period. Subjects that do not rollover into Trial 405-201-00015 must be willing to discontinue all prohibited psychotropic medications starting from the time of signing the informed consent until after the follow-up telephone call 10 days after the last dose of IMP.
 
Subjects must have a Clinical Global Impression-Severity of Illness Scale (CGI-S) score of ≥ 4 (\geq moderate impairment) at baseline.

Inclusion/Exclusion Criteria:	
Key inclusion criteria are described under Subject Population in this synopsis. Key exclusion criteria include the following:
 
Screening:
 
 • Subject has a DSM-5 diagnosis of Other Specified or Unspecified Attention Deficit/Hyperactivity Disorder. • Subject has a current comorbid psychiatric disorder that either could be expected to require treatment with medications prohibited in this trial, or to confound efficacy or safety assessments. Examples include, but are not limited to, psychotic disorder (current or lifetime), bipolar disorder (current or lifetime), generalized anxiety disorder, obsessive-compulsive disorder, panic disorder, a current major depressive episode, or posttraumatic stress disorder, as established by the MINI. • In the opinion of the investigator, subject has not derived significant therapeutic benefit from 2 or more ADHD therapies of 2 different classes (eg, amphetamine and methylphenidate, or amphetamine and atomoxetine) given with an acceptable dose and duration during adulthood (aged 18 or older). NOTE: If subject has not derived significant therapeutic benefit due to an inability to tolerate side effects, eligibility can be discussed on case-by-case basis with the medical monitor.

Protocol 405-201-00014

- Subjects that have a positive alcohol test (via breathalyzer or blood), a positive drug screen for cocaine, or other illicit drugs (excluding marijuana). Subjects with a positive drug screen for confirmed prescription or over-the-counter (OTC) use of ADHD medications at screening will be required to undergo a washout period. NOTE: Subjects that test positive for marijuana may be permitted to be enrolled if they have no evidence of a substance use disorder, and if they agree to refrain from use for the duration of the trial. Allowance for subjects testing positive for marijuana at screening require explicit approval from the medical monitor.

Single-blind placebo run-in:

- Subjects who have a positive alcohol test (via breathalyzer or blood), a positive drug screen assessed prior to Visit 2 for cocaine, other illicit drugs (including marijuana), or prescription or OTC ADHD medications will be screen failed. This includes medications such as opioids or benzodiazepines taken without prescription.
- Subjects with a $\geq 30\%$ improvement in the (18 item) ADHD Symptoms score of the Adult ADHD Self Report Scale (ASRS) compared with the score at screening will be screen failed, and not eligible for rescreening.

Baseline:

- Subjects who have a positive alcohol test (via breathalyzer or blood), a positive drug screen assessed prior to the baseline visit for cocaine, other illicit drugs (including marijuana), or prescription or OTC ADHD medications will be early terminated. This includes medications such as opioids or benzodiazepines taken without prescription.
- Subjects with a $\geq 30\%$ improvement in the (18 item) ADHD Symptoms score of the ASRS compared with the score at the start of single-blind placebo run-in will be early terminated.
- In the opinion of the investigator, the subject is unable to adhere to the treatment regimen or other requirements outlined in the protocol.

Trial Site(s):	The trial is expected to enroll subjects at approximately 40 sites in the United States.
----------------	--

Protocol 405-201-00014

Investigational Medicinal Product(s), Dose, Dosage regimen, Treatment period, Formulation, Mode of Administration:	
The IMP will be supplied as weekly blister cards. All subjects will begin oral BID dosing with single-blind matching placebo on Visit 2 (Day –7) and continue through Visit 3 (baseline).
 
Trial assignments for the double-blind treatment period will be made once eligibility is confirmed. Eligible subjects will be randomized in a 1:1:1 ratio at baseline (Visit 3) to one of the following 3 treatment groups:
 
 • Centanafadine SR 200 mg • Centanafadine SR 400 mg • Matching placebo 
Subjects randomized to receive the target TDD of 200 mg centanafadine SR will start at the target dose on Day 1 of the double-blind treatment period and remain there for the duration of the trial. Subjects randomized to receive a TDD of 400 mg centanafadine SR will receive a TDD of 200 mg centanafadine SR on Day 1 of the double-blind treatment period for 7 days before they are escalated to their target TDD of 400 mg on Day 8 for the duration of the trial.
 
  
 Day(s)	Time	Total Daily Dose	
 
 200 mg Target	400 mg Target	
   
 1 through 7	2 tablets orally in morning	1 × 100 mg + 1 × PBO tablet	1 × 100 mg + 1 × PBO tablet	
 
 2 tablets orally 4-6 hr later	1 × 100 mg + 1 × PBO tablet	1 × 100 mg + 1 × PBO tablet	
 
 8 and thereafter	2 tablets orally in morning	1 × 100 mg + 1 × PBO tablet	2 × 100 mg	
 
 2 tablets orally 4-6 hr later	1 × 100 mg + 1 × PBO tablet	2 × 100 mg	
  
 
PBO = placebo.
 
Neither the investigator nor the subject will be aware of the treatment assignment after randomization. All doses of centanafadine SR and matching placebo should be taken orally BID and can be administered without regard to meals, and should be taken at approximately the same time each day, with the first dose taken in the morning. The second dose should be taken 4 to 6 hours after the morning dose is administered.
 
The total duration of the double-blind treatment period will be 6 weeks for all randomized subjects.
	Day(s)	Time	Total Daily Dose		200 mg Target	400 mg Target	1 through 7	2 tablets orally in morning	1 × 100 mg + 1 × PBO tablet	1 × 100 mg + 1 × PBO tablet	2 tablets orally 4-6 hr later	1 × 100 mg + 1 × PBO tablet	1 × 100 mg + 1 × PBO tablet	8 and thereafter	2 tablets orally in morning	1 × 100 mg + 1 × PBO tablet	2 × 100 mg	2 tablets orally 4-6 hr later	1 × 100 mg + 1 × PBO tablet	2 × 100 mg
Day(s)	Time			Total Daily Dose																	
		200 mg Target	400 mg Target																		
1 through 7	2 tablets orally in morning	1 × 100 mg + 1 × PBO tablet	1 × 100 mg + 1 × PBO tablet																		
	2 tablets orally 4-6 hr later	1 × 100 mg + 1 × PBO tablet	1 × 100 mg + 1 × PBO tablet																		
8 and thereafter	2 tablets orally in morning	1 × 100 mg + 1 × PBO tablet	2 × 100 mg																		
	2 tablets orally 4-6 hr later	1 × 100 mg + 1 × PBO tablet	2 × 100 mg																		

Protocol 405-201-00014

Trial Assessments:	
Efficacy: AISRS, CGI-S, Clinical Global Impression (CGI) Change from Baseline
 
Pharmacokinetic: Sparse pharmacokinetic (PK) samples will be taken for determination of concentrations of centanafadine and metabolite(s) in plasma on Days 7, 14, 28, 42/end of treatment/early termination (ET), and 49/7-day follow-up. Samples collected at Day 14 and Day 42/ET should be taken concurrently with the serum chemistry sample.
 
Safety: Adverse event (AE) reporting (including evaluations for rash, AEs related to abuse potential, and AEs involving medication handling irregularities), clinical laboratory tests, physical examinations, vital sign measurements, electrocardiograms (ECGs), assessments of withdrawal (Study Medication Withdrawal Questionnaire [SMWQ]), and suicidality (Columbia-Suicide Severity Rating Scale [C-SSRS]).
 
Screening/Other: ADHD Impact Module - Adult (AIM-A) and ASRS. A whole blood sample to extract deoxyribonucleic acid (DNA) for genotyping and a future biospecimen research sample will be collected at baseline.

--------------------	---

Protocol 405-201-00014

Criteria for Evaluation:	
Primary Efficacy Endpoint:
 
The primary efficacy endpoint is the change from baseline at Day 42 in the AISRS total score.
 
Key Secondary Efficacy Endpoint:
 
The key secondary efficacy endpoint is change from baseline at Day 42 on the CGI-S.
 
Other Efficacy Endpoints:
 
 • Change from baseline in AISRS total score for every scheduled visit; • Change from baseline in the Inattentive subscale and Hyperactivity-Impulsive subscale scores of the AISRS for every scheduled visit; • Change from baseline in CGI-S score for every scheduled visit; • CGI Change from Baseline score at each scheduled visit; • Percentage of responders at each post-baseline visit, where a responder is defined as a subject with a CGI Change from Baseline score of 1 or 2 OR a $\geq 30\%$ improvement in ADHD symptoms compared with baseline as measured by the AISRS total score. 
Exploratory Efficacy Endpoints:
 
The exploratory endpoints are the change from baseline to Day 28 and Day 42 in the AIM-A and the ASRS total score and subscale scores.
 
Safety Endpoints:
 
Standard safety variables will include AEs (including evaluations for rash, AEs related to abuse potential, and AEs involving medication handling irregularities), clinical laboratory tests (hematology, serum chemistry, and urinalysis), physical examinations, vital sign measurements, ECGs, assessments of withdrawal (SMWQ), and suicidality (C-SSRS).
 
Abuse-related AEs and AEs involving medication irregularities will be recorded verbatim on source documentation with detailed narratives.

--------------------------	--

Protocol 405-201-00014

Statistical Methods:

A sufficient number of subjects will be enrolled and randomized to achieve approximately 405 evaluable subjects in the double-blind treatment period (ie, subjects with an AISRS total score at baseline and at least 1 subsequent AISRS total score in the double-blind treatment period). After allowance of 10% nonevaluable subjects in the double-blind treatment period, the total number of subjects to be randomized is 450 subjects (150 subjects in each treatment arm). In order to ensure 405 evaluable subjects, the number of nonevaluable subjects will be monitored in a blinded manner on an ongoing basis during the trial. The power and sample size were obtained using the PASS 14 (2015) statistical computing software.

The primary efficacy endpoint is the change from baseline to Day 42 in AISRS total score. The estimand for the primary efficacy analysis is the difference in outcome improvement if all subjects tolerated and adhered to their treatment. This approach is Estimand #3, recommended by the 2010 National Academy of Sciences' National Research Council report on prevention and treatment of missing data and International Council for Harmonisation E9 (R1) "Addendum to Statistical Principles for Clinical Trials on Choosing Appropriate Estimands and Defining Sensitivity Analyses in Clinical Trials". This estimand focuses on the efficacy of centanafadine (SR 200mg TDD or SR 400mg TDD) in change from the baseline in AISRS total score. The objective of this trial is consistent with the election of an efficacy rather than effectiveness estimand.

The primary efficacy analysis will be performed by fitting a mixed-effect model repeated measures analysis with an unstructured variance covariance structure in which the change from baseline in AISRS total score at the scheduled double-blind treatment period visits will be the dependent variable based on the observed-case data set. The model will include fixed class effect terms for treatment, trial center, visit day, and an interaction term of treatment by visit day. The model will also include baseline values of AISRS total score and the interaction term of baseline values of AISRS total score by visit day as covariates. The primary comparison between the centanafadine (200 mg TDD or 400 mg TDD group) and the placebo group at Day 42 in the double-blind treatment phase will be estimated as the difference between Least Squares means utilizing the computing software SAS procedure PROC MIXED.

Protocol 405-201-00014

	
The comparison between centanafadine 200 mg TDD or 400 mg TDD group and placebo group will be tested at a significance level of 0.05 (2-sided) in the order of 1) 400 mg versus placebo, and 2) 200 mg versus placebo. Additional details will be provided in the statistical analysis plan (SAP). Based on the results at various dose strengths from phase 2 centanafadine trials, it is reasonable to expect a treatment difference of 5 points with a standard deviation (SD) of 12.5 in the mean change from baseline to Day 42 on AISRS total score in either the 200 mg TDD or 400 mg TDD arms. The planned sample size of 405 evaluable subjects (135 in each treatment arm) will yield at least 90% power to detect the treatment effects at a 2-tailed significance level of 0.05. The 2-sided alpha level for the final analysis is 0.05.
 
Descriptive statistics will be provided for all efficacy and safety variables in general. Continuous variables will be summarized by tabulations of mean, median, range, and SD. Tabulations of frequency distributions will be provided for categorical variables.

Trial Duration:	
A total of up to 1150 male and female subjects are planned to be screened in order to randomize approximately 450 subjects to yield approximately 292 completers. Individual participation for all subjects in the trial is 12 to 13 weeks, consisting of an up to 28-day screening period, a 1-week single-blind placebo run-in period, a 6-week double blind treatment period, and a 7-day follow-up period (follow-up telephone calls at 1, 3, and 5 days after the last dose of IMP, and in-clinic visits 2 and 7 days after the last dose of IMP) for all subjects. For subjects who early terminate or decline participation in the open-label trial, they will be required to participate in an additional follow-up telephone call 10 days after the last dose of IMP.

Protocol 405-201-00014

Table of Contents

Protocol Synopsis	2
Table of Contents	11
List of In-text Tables	16
List of In-text Figures	17
List of Appendices.....	18
List of Abbreviations and Definitions of Terms	19
1 Introduction	21
1.1 Nonclinical Data.....	22
1.2 Clinical Data.....	23
1.3 Known and Potential Risks and Benefits	23
2 Trial Rationale and Objectives.....	25
2.1 Trial Rationale	25
2.2 Dosing Rationale	25
2.3 Trial Objectives	26
3 Trial Design	26
3.1 Type/Design of Trial	26
3.2 Trial Treatments	29
3.2.1 Single-blind Placebo Run-in Period	29
3.2.2 Double-blind Treatment Period	29
3.3 Trial Population	30

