3.2.2 Double-blind Treatment Period

Trial assignments for the double-blind treatment period will be made once eligibility is confirmed. Eligible subjects will be randomized in a 1:1:1 ratio at baseline (Visit 3) to one of the following 3 treatment groups:

- Centanafadine SR 200 mg TDD
- Centanafadine SR 400 mg TDD
- Matching placebo

Neither the investigator nor the subject will be aware of the treatment assignment after randomization. All doses of centanafadine SR and matching placebo should be taken orally BID and can be administered without regard to meals, and should be taken at approximately the same time each day, with the first dose taken in the morning. The second dose should be taken 4 to 6 hours after the morning dose is administered.

Subjects randomized to receive the target TDD of 200 mg centanafadine SR will start at the target dose on Day 1 of the double-blind treatment period and remain at that dose for the duration of the trial (Table 3.2.2-1). Subjects randomized to receive a TDD of 400 mg centanafadine SR will receive a TDD of 200 mg centanafadine SR on Day 1 of the double-blind treatment period for 7 days before they are escalated to their target TDD of 400 mg on Day 8 for the duration of the trial (Table 3.2.2-1).

Protocol 405-201-00014

Table 3.2.2-1 Dosing Schedule for Centanafadine SR Tablets			
Day(s)	Time	Total Daily Dose	
		200 mg Target	400 mg Target
1 through 7	2 tablets orally in morning	1 × 100 mg + 1 × PBO tablet	1 × 100 mg + 1 × PBO tablet
	2 tablets orally 4-6 hr later	1 × 100 mg + 1 × PBO tablet	1 × 100 mg + 1 × PBO tablet
8 and thereafter	2 tablets orally in morning	1 × 100 mg + 1 × PBO tablet	2 × 100 mg
	2 tablets orally 4-6 hr later	1 × 100 mg + 1 × PBO tablet	2 × 100 mg

PBO = placebo.

For subjects randomized to placebo, they will take 2 placebo tablets in the morning and 2 tablets in the afternoon for the duration of treatment.

Once the subject is at the target dose, further dose modification is not permitted. Dose modification is not allowed at any time during the trial.

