3.5.2.2 Other Efficacy Endpoints

- Change from baseline in AISRS total score for every scheduled visit;
- Change from baseline in the Inattentive subscale and Hyperactivity-Impulsive subscale scores of the AISRS for every scheduled visit;
- Change from baseline in CGI-S score for every scheduled visit;
- Clinical Global Impression (CGI) Change from Baseline score at each scheduled visit;
- Percentage of responders at each post-baseline visit, where a responder is defined as a subject with a CGI Change from Baseline score of 1 or 2 OR a $\geq 30\%$ improvement in ADHD symptoms compared with baseline as measured by the AISRS total score;

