3.7.1.4 Double-Blind Treatment Period

3.7.1.4.1 Visits 4 through 8

The assessments described for Visits 4 through 8 (Days 7-35) in the Schedule of Assessments (Table 3.7-1) will be completed. The following should also be noted:

- Urine drug screen results from the previous visit will be reviewed. If the subject is positive for any prohibited medications (including medications for the treatment of ADHD, see Section 4.1), the subject will be early terminated, and the procedures outlined in Section 3.7.1.4.2 will be completed.
- At each visit dosing cards from the prior week will be returned; accountability and compliance will be verified.
- Sparse PK samples will be collected at Visits 4 (Day 7), 5 (Day 14), and 7 (Day 28).
- Subjects will receive a dosing card for dosing at each visit for the next week, and will be instructed to start dosing from the new card on the following day, and to take their doses at approximately the same time every day.

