8.1.2 Technical Computation Details for Primary Efficacy Analysis

The SAS code for the PROC MIXED procedure to carry out the above MMRM analysis with an unstructured variance covariance structure is illustrated as follows:

```
proc mixed;
  class treatment center visit subjid;
  model change=treatment center visit treatment*visit baseline*visit / s cl
  ddfm=kenwardroger;
  repeated visit /type=un subject=subjid r rcorr;
```

SAP 405-201-00014

```
lsmeans treatment*visit / pdiff cl alpha=0.05 slice=visit;
run;
```

where baseline is the last AISRS Total score prior to the first dose of double-blind IMP in the double-blind treatment period.

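### Day 7 in the by-visit analyses: the 400 mg versus placebo contrast measures 200 mg/day, so both active arms should be pooled and labelled as 200 mg/day at that visit

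*Protocol*

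**What the plan says.** **Dosing.** Under Protocol 3.2.2, subjects randomized to 400 mg "will receive a TDD of 200 mg centanafadine SR on Day 1 of the double-blind treatment period for 7 days before they are escalated". Table 3.2.2-1 lists identical tablets for the two active arms on Days 1 to 7. The Days 1 to 7 card is given out at baseline (3.7.1.3). At Visits 4 to 8 subjects receive the next card and "will be instructed to start dosing from the new card on the following day" (3.7.1.4.1). A rating at a Visit 4 held as scheduled therefore comes before the first 400 mg dose.

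**Analysis.** The model in the Synopsis and Protocol 7.3.1 is a repeated-measures model: "The model will include fixed class effect terms for treatment, trial center, visit day, and an interaction term of treatment by visit day". The SAP 8.1.2 code is "model change=treatment center visit treatment*visit baseline*visit". The treatment factor has three levels at all six visits, so the active arms have separate Day 7 means.

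**Endpoints.** Protocol 3.5.2.2 lists "Change from baseline in AISRS total score for every scheduled visit", and the same for the AISRS subscales and CGI-S. Protocol 7.3.2.2 and SAP 8.3 test these with the primary model at a nominal 0.05, without multiplicity adjustment and outside the fixed sequence. Neither document pools the arms at Day 7 or notes that both were then on 200 mg/day.

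**The concern.** Randomization, blinding and identical tablets make the two active arms one treatment group at a scheduled Day 7 rating. The plan gives that group two labels. The by-visit tables are where onset and dose response will be read, and a Day 7 row for 400 mg invites the reader to see an early effect of 400 mg. Protocol 2.2 reasons the other way: it takes Day 7 phase 2 data from subjects still titrating as evidence on the lower dose.

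The second cost is precision. Each Day 7 contrast uses half of the available 200 mg/day subjects. Day 7 and Day 42 scores are also correlated, so the known equality at Day 7 carries some information on Day 42 that the planned model does not use.

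**Working it through.** **1. The plan's own power figure.** The inputs are in Protocol 7.1: "it is reasonable to expect a treatment difference of 5 points with a standard deviation (SD) of 12.5", with 135 evaluable subjects per arm.
- SE = 12.5 × √(2/135) = 1.521.
- Power = Φ(5/1.521 − 1.96) = 90.8% (90.6% with the t distribution).
- 405/(1 − 0.10) = 450 randomized.

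The claim that the sample "will yield at least 90% power to detect the treatment effects at a 2-tailed significance level of 0.05" reproduces without any Day 7 constraint.

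**2. Day 7, from the design alone.** With n per arm and variance v:
- One active arm versus placebo: v(1/n + 1/n) = 2v/n.
- Both active arms pooled versus placebo: v(1/(2n) + 1/n) = 1.5v/n.
- SE ratio = √0.75 = 0.866, a 13% reduction that depends on no trial result.

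**3. Day 7 in AISRS points.** The inputs come from the output appended to the SAP: UN(1,1) = 43.6133 in STAT-4.1.1; Day 7 counts of 137 (200 mg), 139 (400 mg) and 139 (placebo) in STAT-4.7.
- 200 mg arm: √[43.6133(1/137 + 1/139)] = 0.795 (printed 0.796).
- 400 mg arm: √[43.6133(2/139)] = 0.792 (printed 0.799).
- Pooled: √[43.6133(1/276 + 1/139)] = 0.687.
- Printed contrasts: −1.93 (p = 0.0157) and −1.81 (p = 0.0240). Their average is −1.87; −1.87/0.687 = −2.72, p about 0.007.

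The two printed contrasts differ by 0.12, which is unsurprising for two samples of one treatment.

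**4. Day 42, if a shared Day 7 mean were modelled.** For complete data the active-arm Day 42 variance is multiplied by 1 − ρ²/2 and the placebo variance is unchanged. The contrast variance is therefore multiplied by 1 − ρ²/4, where ρ is the Day 7 to Day 42 correlation.
- Planning range: ρ = 0.3 gives a 2% reduction, ρ = 0.7 gives 12%.
- Pooled covariance: ρ = 38.2789/√(43.6133 × 108.84) = 0.556, giving 7.7%.
- CGI-S (STAT-5.1): ρ = 0.2947/√(0.3911 × 0.9541) = 0.48, giving 5.8%.

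With the full 6 × 6 covariance, the STAT-4.7 counts and monotone dropout assumed, generalized least squares gives these Day 42 SEs:

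| Contrast with placebo | Printed | Planned model, rebuilt | Shared Day 7 mean | Variance reduction |
|---|---|---|---|---|
| 200 mg | 1.294 | 1.300 | 1.251 | 7.3% |
| 400 mg | 1.322 | 1.319 | 1.273 | 6.9% |

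The arm-specific covariances in STAT-4.10 have ρ = 0.61 (200 mg), 0.46 (400 mg) and 0.60 (placebo). The same calculation then gives reductions of about 11% for 200 mg and 4% for 400 mg. Those covariances fit better: −2 log-likelihood falls by 13567.2 − 13465.6 = 101.6 for 63 − 21 = 42 extra parameters.

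**The case against.** The strongest reply is that nothing planned is invalid. The arms are target-dose regimens, subjects are analysed as randomized, and a comparison of the 400 mg regimen with placebo one week in is a legitimate contrast. The escalation is stated repeatedly, and SAP 9.10 tabulates mean daily dose by week and arm. Day 7 is nominal and ungated. All of this stands. It makes the point one of labelling and precision; it does not remove it, because the by-visit efficacy tables carry the 400 mg label without that explanation.

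A reader might go further and infer that the Day 42 tests are biased or underpowered, or that the primary model should be replaced by one with a shared Day 7 mean. The documents do not support this. The free interaction leaves the Day 42 contrasts unbiased, and the stated power never relied on a constraint. What is forgone is optional, and with arm-specific covariances it is smallest for 400 mg, the first test in the sequence.

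The equality is also less secure than a constrained baseline, because it concerns a post-randomization visit and depends on conduct. SAP Table 10-1 maps Days 2 to 10 to Day 7 and takes the last value, so a rating on Day 9 or 10, for example at early termination, can follow escalation. Visit 4 may fall on Day 8. For such a visit the Day 8 escalation in Table 3.2.2-1, the card covering Days 1 to 7 and the instruction to start the new card the next day do not agree on Day 8 dosing; these passages must be reconciled. Removing post-escalation ratings from the 400 mg arm alone would be arm-specific selection after randomization, so equality would no longer follow from randomization.

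**Conclusion.** The point holds as a cheap improvement to the by-visit analyses of AISRS total, its subscales and CGI-S. If Visit 4 runs as scheduled, the Day 7 contrast for 400 mg contains no 400 mg exposure. Pooling gives one correctly labelled comparison with a 13% smaller SE. That percentage rests only on equal allocation, a common variance and identical dosing up to the rating; the AISRS figures rest on results produced on 31 August 2020, after SAP approval on 26 May 2020.

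It is not a finding against the primary or key secondary analysis. The Day 42 variance gain from a shared Day 7 mean is about 7% with the pooled covariance, about 4% (400 mg) and 11% (200 mg) with arm-specific covariances, and 2% to 12% over the assumed planning range of ρ. That does not justify replacing a registrational primary model with one that needs equality after randomization.

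**What to change.** In Protocol 7.3.2.2 and SAP 8.3:

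1. At Day 7, test pooled centanafadine 200 mg/day (both active arms) against placebo. This can be one added estimate from the planned model: the average of the two active Day 7 means minus the placebo mean.
2. Keep the by-arm Day 7 values as descriptive figures, with a footnote that both arms were on 200 mg/day.
3. List every 400 mg-arm rating in the Day 2 to 10 window made after the first 400 mg dose. Show the pooled result with and without Day 9 and 10 ratings, removed in all three arms alike.
4. Keep the planned model as primary for AISRS and CGI-S. If the Day 42 gain is wanted, prespecify the shared-Day-7-mean model as supportive only, and state how post-escalation ratings enter it.

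The cost is one extra contrast, a footnote and a short listing, with no new data. The downside is that Day 7 is no longer tested separately by arm.
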